7.0 HUMAN SUBJECT RESEARCH and ETHICAL CONCERNS

Signed consent in English will be obtained from each participant / patient at the time of enrollment. The objectives of the study and the data collection procedures will explained to every prospective participant before study enrollment. An IRB-approved consent document will be used for protocols. Consent for the patients includes the right of the subject:

- To either withdraw or refuse participation without prejudice at any time during the study;
- To voluntarily participate in the research;

- To receive new information about the study as it becomes available;
- To understand the procedures, risks, and benefits;
- To maintain confidentiality of personal medical information.

8.0 PROTECTION AGAINST RISK

The proposed study involves changes in provision of program services to study participants. Description of random and blinded nature of the protocols will be explained by the physician in charge of the participant. To avoid or minimize potential risks, frequent monitoring for adverse events will be performed by study staff and the PI.

Risks of clobetasol proprionate include skin irritation, burning, rash and change in skin pigmentation.

Potential adverse reactions to laser use include ocular laser exposure which will be minimized with the use of protective eyewear with an optical density of 4x the treatment wavelength. Pain or mild to moderate discomfort, erythema, swelling, blistering, itching, numbness, change in pigmentation, scarring, and burns are other adverse events including as well as painful intercourse, change (postive or negative) in sexual response, including arousal around clitoris and orgasm. These risks will be minimized with laser use per manufacture instructions with trained personel and avoidance of laser treatment within 5mm of clitoral glans and hood. All known risks will be disclosed to the participants via the informed consent process. All study participants will be closely monitored post treatment for adverse events.

All known risks will be disclosed to the participants via the informed consent process. All study participants will be closely monitored post treatment for adverse events. All study investigators will receive extensive training on the study protocol. Attending staff/surgeons will also receive training on how to operate the laser and the appropriate settings for the vulvar treatment, supervised by the study mentor. Serious adverse events are defined as any untoward medical occurrence that (1) results in death, (2) is life-threatening, (3) requires inpatient hospitalization (4) results in persistent or significant disability or incapacity, (5) is a congenital anomaly/birth defect, or (6) is another medically important condition.

Data safety and Monitoring Board (DSMB) headed by [name], Director of Gynecologic Oncology at MedStar Washington Hospital Center, will review all serious adverse events, including any untoward occurrence that (1) results in death, (2) is life threatening, (3) requires inpatient hospitalization, (4) results in permanent or significant disability or incapacity, and (5) is another medically important condition. All ongoing data will be analyzed once half of patients have been recruited and at completion of recruitment and study conclusion.

9.0 SOURCES OF MATERIALS

Medical record data and program records will be obtained for each participant. Demographic information and personal history will be obtained by interview. Study data, such as information obtained at follow-up assessment examination and interviews, will be obtained according to the time-frame specified in the protocol.

10.0 CONFIDENTIALITY

This research staff will take every precaution to protect the confidentiality of the collected data. All personnel with access to data collected have completed the Program for Ethics Education in Research training with the appropriate HIPAA certification. Completed data forms will be placed in locked file cabinets, and only authorized staff members will have access to the data. The data will be compiled into a computerized database and will be stored on computers used exclusively for research studies and are safeguarded by passwords known only to authorized personnel. Photo documentation is to capture isolated vulvar and perineal area. Other identifiable body parts including patient's face will not be included in photographs. Photographs used as

part of photo documentation will be uploaded from digital camera after each encounter. The photograph file will be labeled with non identifiable patient number. Digital camera photo card will be cleared and photographs stored on research computers safeguarded by passwords. Fujifilm JX665 Digital Camera will be stored with storage card in locked file cabinets, and only authorized staff members will have access. Data are analyzed collectively. No personal identities are revealed to the statistician. The data used are obtained strictly for the purposes of the research in question. Any printout information and photographs will be destroyed once the project is completed and reports written.

11.0 TIMING OF STUDY and RECRUITMENT

The study investigators plan to start recruitment in August 2015. Study recruitment is expected to be complete within 5 years by August 2018. One year follow-up will be complete by August 2019. This study will be complete and the results analyzed by the primary investigator, [name].

12.0 STATISTICAL ANALYSIS

Statistical intention-to-treat and per protocol analysis will be completed in R (version 3.4, Vienna, Austria 2017) with demographic and questionnaire scores reported as means and standard deviations or medians and interquartile ranges. Chi square or Fisher's exact, two-sample t-test and Mann Whitney U will be used to compare categorical, continuous, and non-parametric variables, respectively. D-Agostino test will be used to assess normality. Two-way ANOVA analysis of mean Skindex-29 score improvement based on prior steroid exposure and treatment group will be performed.

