3.0 STUDY DESIGN

Women presenting to the urogynecology clinic will be screened for lichen sclerosus. Vulvar biopsy will be performed for confirmation, and, if eligible, the patient will be consented to undergo baseline questionnaires, photodocumentation of vulvar lesions and randomization. Patient will be randomized to monthly LASER treatment for 3 months or topical STEROID therapy (temovate propionate .05% ointment nightly for one month, three times weekly for 2 additional months, then as needed) in a 1:1 ratio using a computer generated randomization schedule. Grouping assignments will be kept in sealed consecutively numbered, opaque envelopes. Because of the nature of the treatment, it will not be possible to blind patients but the assessor will be blinded to the intervention.

Patient questionnaires include multiple validated scales and surveys to provided reproducible measures of vulvar symptoms as primary and secondary outcomes. Questionnaires will be completed at the intake visit, repeated at 12 weeks after treatment is completed or 6 months from intake, and one year follow up. Subjective symptoms including vulvar itching, vulvar burning, vulvar irritation, pain with intercourse, tearing of the vulvar skin, painful urination, and painful defecation will be rated with a validated visual analog scale (VAS), scaled 0-10, see appendix 1. Higher values correspond to more bothersome symptoms. The Skindex-29 questionnaire is a subjective measure of skin symptoms validated against the Medical Outcomes Study 36-item Short-Form Survey (SF-36)¹⁷, appendix 2. The Skindex-29 was developed in dermatology and modified for use in vulvadynia¹⁸. The Skindex-29 is scored as a sum expressed on a 100-point scale with higher scores indicating lower quality of life. Validated quartiles are used to characterize disease symptoms, emotions, functioning, and overall score as either very little, mild, moderate, or severe¹⁹. Secondary outcomes of patient satisfaction and global impression of improvement will be collected using simple validated visual analog scale from 0-5, much worse to much better, appendix 4. A final subjective measure, the Vulvovaginal Symptoms Questionnaire (VSQ), a validated measure of vulvar symptoms, emotions, life impact, and sexual impact in postmenopausal women will be collected a secondary outcome²⁰, appendix 5. A higher total score on the VSQ corresponds to lower quality of life.

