5.0 SAMPLE SIZE CALCULATION

The study will consist of 2 study groups (LASER vs STEROID therapy). We expect improved subjective and objective results in the LASER group at 3 months post treatment or 6 months from enrollment compared with the STEROID group.

This study is designed as a two-group randomized clinical trial. Sample size calculations were conducted using the absolute change in the Skindex 29 as the primary end point. Our study will reach 80% power to detect a mean difference of 16 points on the Skindex 29 (sd=22 for both groups)²² between the study groups with 24 patients in each group, or 48 in total based on a one-sided two-sample t-test with alpha=0.05. By accounting for 10% attrition, we propose to recruit 52 patients to the study to be randomized with a 1:1 ratio to each group, with a blocked component for those who used topical clobetasol in the past. The Skindex-29 has validated cutoff categories for mildly, moderately, and severely impaired health related quality of life scores, the mean difference between each quality of life measure overall score is between 6 and 7. Therefore, powering the study for a detection of mean difference of 16 points should measure significant quality of life improvement.^{23,24}

Study Timeline:

	Intake Visit	Day 0	2 weeks	4 weeks-14 weeks	6 months	1 year
Vulvar biopsy (if never completed)	X					
Vaginal STEROID or LASER			STEROID daily x 4 weeks LASER monthly x 3 months	STEROID three times weekly x 8 more weeks, then as needed LASER STOP at 12 weeks		
Vaginal Health Index scale (VHIS)		X			X	x
SkIndex-29 Vulvar QoL Questionnaire Vulvovaginal Symptoms Questionnaire (VSQ)		X			X	x
Telephone call to check compliance and answer questions			X	X (8 weeks)		
Photodocumentation		X			X	x
Questionnaire of patient global impression of improvement and satisfaction PGI-I					X	x

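### Baseline Skindex-29 enters the planned analyses only by subtraction, never as a covariate: adjusting is worth roughly 0 to 10 points of power, and the present plan is not an error

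*Combined protocol and SAP*

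**What the plan says.** Section 5.0 of the combined protocol and SAP fixes the endpoint: "Sample size calculations were conducted using the absolute change in the Skindex 29 as the primary end point". It then gives the design values: "Our study will reach 80% power to detect a mean difference of 16 points on the Skindex 29 (sd=22 for both groups", "between the study groups with 24 patients in each group, or 48 in total based on a one-sided two-sample t-test with alpha=0.05". It does not say whether 22 is the SD of change or of a score at one visit. Randomisation is 1:1 "with a blocked component for those who used topical clobetasol in the past".

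Section 12.0 lists the analyses: "two-sample t-test and Mann Whitney U will be used to compare categorical, continuous, and non-parametric variables, respectively"; "D-Agostino test will be used to assess normality"; and "Two-way ANOVA analysis of mean Skindex-29 score improvement based on prior steroid exposure and treatment group will be performed". The factors in that ANOVA are treatment and prior steroid exposure. Baseline score is not among them, and no regression, ANCOVA or mixed model with baseline as a covariate appears anywhere.

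The baseline score is available. In Section 3.0, "the patient will be consented to undergo baseline questionnaires, photodocumentation of vulvar lesions and randomization", and Section 4.0 excludes women whose overall Skindex-29 is below 21, so eligibility cannot be decided without it.

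**The concern.** Analysing follow-up minus baseline is the same as fixing the regression slope of follow-up on baseline at 1. When the true slope is below 1, subtraction over-corrects for chance baseline differences and carries extra baseline noise into the outcome. A model that estimates the slope removes that noise.

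Validity is not at stake. Under randomisation the comparison of changes is unbiased and keeps its type I error. What is at stake is precision in a trial with little to spare: 24 women per arm give just under 80% power on the plan's own assumptions. If the slope is clearly below 1, an adjusted analysis gives a narrower interval from the same data. If it is close to 1, nothing is gained and up to about 1 point of power is lost.

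**Working it through.** **The plan's own figure.** Inputs from Section 5.0: difference 16, SD 22, one-sided 5%, power 80%.

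- Normal approximation: n per arm = 2 × (1.645 + 0.842)² × 22² / 16² = 23.4, rounded up to 24. This reproduces the plan.
- Noncentral t: noncentrality = 16 / (22 × √(2/24)) = 16 / 6.35 = 2.52 on 46 df, so power = 79.9%.

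**Where the gain comes from.** With slope b of follow-up on baseline,

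Var(change) = residual variance + (1 − b)² × Var(baseline).

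ANCOVA works with the residual variance alone. The gain disappears as b approaches 1, and it shrinks when the entry cut-off narrows the baseline spread.

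**Assumptions.** The documents give no correlation, baseline mean or follow-up SD. I took a normal baseline with mean 45 restricted to 21–100, and follow-up = constant + slope × baseline + normal error, with slope = correlation × (follow-up SD / baseline SD). Correlations, SDs and means are those of the underlying distribution before the cut-off. Follow-up was not limited to 0–100. Each setting used 40,000 simulated trials (20,000 for baseline means 35 and 55); the Monte Carlo error of each power is at most about 0.3 points. The t-test on change (46 df) was compared with a linear model on treatment, baseline and a balanced non-prognostic stratum (44 df).

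**(A) 22 is the SD of change, equal underlying SDs.** The score SD is solved so that the SD of change after the cut-off is 22. Residual SD = score SD × √(1 − correlation²). Change-score power is 80% and the average 95% half-width 12.7 points throughout.

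| Correlation | Score SD | Residual SD | Power with covariate | Gain (points) | Half-width |
|---|---|---|---|---|---|
| 0.3 | 19.8 | 18.9 | 88.8% | 8.5 | 11.0 |
| 0.5 | 23.3 | 20.2 | 85.0% | 5.1 | 11.8 |
| 0.6 | 25.9 | 20.7 | 83.6% | 3.7 | 12.1 |
| 0.7 | 29.7 | 21.2 | 81.7% | 1.7 | 12.4 |
| 0.8 | 36.0 | 21.6 | 80.4% | 0.4 | 12.7 |

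**(B) 22 is the SD of a single score, equal underlying SDs.** The cut-off reduces the baseline SD to 17.2.

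| Correlation | SD of change | Power, change | Power with covariate | Gain (points) |
|---|---|---|---|---|
| 0.3 | 24.2 | 72.7% | 82.1% | 9.5 |
| 0.5 | 20.9 | 83.6% | 88.4% | 4.8 |
| 0.6 | 18.9 | 89.5% | 92.4% | 2.8 |
| 0.7 | 16.5 | 95.4% | 96.4% | 1.1 |
| 0.8 | 13.6 | 99.1% | 99.3% | 0.3 |

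Gains are taken before rounding. Hand check at correlation 0.5: the residual SD is 22 × √0.75 = 19.05, and √(19.05² + 0.5² × 17.2²) = 20.9, as tabulated.

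**Unequal SDs.** Gains in points at correlations 0.3, 0.5, 0.6, 0.7, 0.8:

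| Follow-up SD | (A) | (B) |
|---|---|---|
| 20% larger | 5.9, 2.1, 0.9, −0.2, −0.8 | 5.8, 2.2, 1.2, −0.1, −0.3 |
| 20% smaller | 12.2, 8.8, 7.4, 5.3, 3.4 | 11.8, 6.4, 3.8, 1.5, 0.2 |

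With the larger follow-up SD the slope is 0.7 × 1.2 = 0.84 and 0.8 × 1.2 = 0.96 at the two highest correlations, which is why the gain vanishes. With equal SDs and baseline mean 35 or 55, the gain runs from 0.1 to 10.5 points.

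**Type I error** at zero difference (score SD 22; correlation 0.3, 0.5, 0.7; follow-up SD equal or 20% larger): 4.9–5.1% for the change score and 4.8–5.1% for ANCOVA.

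**Closed-form cross-check without the cut-off.** With equal SDs and 22 as the SD of change, the ANCOVA SD is 22 × √((1 + correlation)/2). The gains are 1.7 points at correlation 0.9, 5.4 at 0.7, 9.0 at 0.5 and 12.5 at 0.3. They exceed table (A) because they ignore the cut-off, so the simulated figures are the more cautious.

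**The case against.** The strongest reply is that this is a preference. The planned analysis is valid, matches the endpoint the trial was sized on, and reaches its stated power if 22 is the SD of change. At correlation 0.7 or above with an equal or larger follow-up SD, the gain is under 2 points or slightly negative. The size of the gain rests on a correlation, an SD ratio and a baseline mean that the documents do not give. That is all true. It is why the point is framed as an improvement and the gain as a range.

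The correlations also need care in use. They apply before the cut-off: in (A), 0.3 to 0.8 corresponds to about 0.25 to 0.61 among eligible women, so a correlation observed in enrolled patients should not be read straight into the table. An underlying SD of 36 around a mean of 45 is implausible on a 100-point scale, and that row is one of those with almost no gain. Unbounded follow-up is a further simplification: if the control mean fell 10 points from 45, about 3–5% of simulated control scores would be below zero.

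Two textual points stand as drafting matters. Section 12.0 does not say whether the t-test and Mann-Whitney test compare changes or follow-up scores; I infer change from Section 5.0. If follow-up scores were meant, those tests would not use baseline at all, and the lack of a covariate would remain. Section 3.0 places the questionnaires at intake, whereas the schedule in Section 5.0 puts Skindex-29 at Day 0. The cut-off still guarantees a screening score, but the plan must say which score is the covariate.

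**Conclusion.** The concern holds. No planned analysis estimates the slope on baseline Skindex-29, and the score needed to do so is already collected. The present analysis is valid; the loss is one of precision. At 24 per arm, difference 16 and one-sided 5%, adjustment is worth roughly 0 to 10 points of power. The settings examined run from −0.8 to +12.2, so 10 is a summary and not a ceiling. The gain is largest with low correlation or a smaller follow-up SD, and about zero with high correlation or a larger follow-up SD.

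The balance favours the change: a possible gain of several points against a loss of about 1 point at worst. It should be made, but the trial does not fail without it. Confidence in the size is moderate, because the quantities that determine it are assumed.

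**What to change.** In Section 12.0, name one primary analysis: a linear model of the 6-month Skindex-29 overall score on treatment, the pre-randomisation Skindex-29 overall score and the past-topical-clobetasol factor used for blocking. Report the adjusted mean difference in points with its confidence interval whatever the D'Agostino test shows. The trial is sized on a difference in points, and a rank test chosen after a normality check would not estimate that. Keep the unadjusted t-test on change and the Mann-Whitney test as sensitivity analyses.

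Three details should be settled in the same edit:

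- which score is the covariate (intake or Day 0), provided it precedes randomisation;
- whether prior steroid exposure in Section 12.0 is the same factor as past topical clobetasol in Section 5.0;
- the role left for the two-way ANOVA, for example as a secondary analysis.

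The cost is SAP wording. No new data are needed. Two degrees of freedom are spent relative to the t-test (46 to 44); a two-way ANOVA with interaction would already have 44.

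### The blocking factor (past topical clobetasol) is missing from the t-test and loosely renamed in the ANOVA, and no primary Skindex-29 analysis is named; putting the stratum in one named model is a free improvement

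*Combined protocol and SAP*

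**What the plan says.** All references are to the combined protocol and SAP.

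- **Section 3.0 (Study Design)** allocates patients "in a 1:1 ratio using a computer generated randomization schedule". It mentions no stratum or block.
- **Section 5.0 (Sample Size Calculation)** adds the restriction: allocation is 1:1 "with a blocked component for those who used topical clobetasol in the past". Block size and list structure are not given. On the endpoint it states: "Sample size calculations were conducted using the absolute change in the Skindex 29 as the primary end point". The test is a one-sided two-sample t-test at 0.05 with 24 patients per group, and carries no stratum term.
- **Section 12.0 (Statistical Analysis)** opens with "Statistical intention-to-treat and per protocol analysis will be completed in R". It lists tests by type of variable: "two-sample t-test and Mann Whitney U will be used to compare categorical, continuous, and non-parametric variables, respectively". It then gives its one analysis specific to Skindex-29: "Two-way ANOVA analysis of mean Skindex-29 score improvement based on prior steroid exposure and treatment group will be performed".

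Section 12.0 does not define prior steroid exposure. It does not say whether the t-test or the ANOVA decides the primary question, or whether the ANOVA includes an interaction.

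**The concern.** Blocking within past clobetasol users and non-users makes the arms alike on that factor. If the factor predicts improvement, the treatment difference then varies less from trial to trial than it would under simple randomisation. A t-test that omits the factor leaves the between-stratum variance in its error term, so its standard error is too large and the precision bought by blocking goes partly unused.

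The ANOVA could repair this, but its factor carries another name. Section 2.0 (Background and Significance) names mometasone beside clobetasol, and Section 4.0 (Subject Population and Selection Criteria) bars vulvar topical steroids only within 2 months of enrolment. A woman who once used mometasone but never clobetasol is therefore eligible. She would be a non-user at randomisation and could be counted as exposed in the ANOVA.

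With no primary analysis named and the factor undefined, both the model and the coding could be settled after the data are seen, in a trial sized at 48 evaluable patients.

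**Working it through.** **Inputs from Section 5.0.** Difference 16 points, SD 22 in each group, one-sided alpha 0.05, 24 per group.

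**Assumptions (not in the documents).**
- Share of past clobetasol users f = 0.3 to 0.5.
- Difference in mean improvement between strata d = 8 to 16 points.
- The blocked component means balance within each stratum.
- The total SD of 22 includes the between-stratum part.

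**Step 1: the plan's own figure.** The normal-approximation formula gives 24 per group, as stated. For the exact t-test:
- standard error = 22 × √(2/24) = 6.35
- noncentrality = 16 / 6.35 = 2.52 on 46 degrees of freedom
- one-sided power = 79.9%

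The stated 80% reproduces.

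**Step 2: what the stratum would explain.** Between-stratum variance = f(1−f)d², out of 22² = 484.
- Low end (f = 0.3, d = 8): 0.21 × 64 = 13.4, or 2.8% of 484. Residual SD = √(484 − 13.4) = 21.7.
- High end (f = 0.5, d = 16): 0.25 × 256 = 64, or 13.2% of 484. Residual SD = √(484 − 64) = 20.5.

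The actual standard error of the treatment difference under blocking is then 21.7 × √(2/24) = 6.26 at the low end and 20.5 × √(2/24) = 5.92 at the high end. The unadjusted t-test works with about 6.35.

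**Step 3: the two analyses in the blocked trial.** The design was simulated with 24 per arm, balance within strata, total SD 22, a 16-point effect and 40,000 runs per cell:

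| f | d | Unadjusted t-test | Treatment + stratum | Power forgone |
|---|---|---|---|---|
| 0.3 | 8 | 80.0% | 80.7% | 0.7 points |
| 0.5 | 8 | 80.3% | 81.1% | 0.8 points |
| 0.3 | 16 | 81.0% | 83.6% | 2.6 points |
| 0.5 | 16 | 81.1% | 84.4% | 3.3 points |

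Simulation error is about √(0.8 × 0.2/40,000) = 0.2 points per entry. A separate run of the two end cells gave 80.0% to 80.7% and 81.4% to 84.7%, the same differences. With no treatment effect, the unadjusted t-test's one-sided type I error is about 4.7% at the low end and 3.8% at the high end.

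**Step 4: wider range.** With equal strata, and R² the share of outcome variance explained by the stratum:

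| R² | Type I error, t-test | Type I error, adjusted | Power, t-test | Power, adjusted |
|---|---|---|---|---|
| 0 | 4.9% | 4.9% | 79.8% | 79.8% |
| 0.10 | 4.0% | 4.9% | 81.0% | 83.4% |
| 0.30 | 2.4% | 5.1% | 83.9% | 90.9% |

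**Step 5: a broader factor in the model.** If 25% of never-clobetasol women had used another steroid (assumed) and were coded as exposed, power is 81.4% at R² = 0.10 and 86.8% at R² = 0.30. Both lie between the unadjusted test and the true stratum. Type I error is 4.6% and 4.4%.

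**The case against.** The strongest reply is that the plan may already do what is asked. Clobetasol is a steroid, the comparator arm is labelled STEROID, and clobetasol history is the only steroid-history variable tied to randomisation. The ANOVA term may simply be the blocking factor under a looser name. The ANOVA is also the only analysis in Section 12.0 specific to Skindex-29 improvement, whereas the t-test appears in a general list. Sizing on an unadjusted test and analysing with adjustment is ordinary practice.

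Much of this stands. A reader might infer that the ANOVA uses a different factor, or that the t-test is the main analysis. The documents establish neither: the term is undefined, and the t-test's primacy would have to be inferred from the sizing alone. That uncertainty is itself the defect, because the text supports both readings.

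A reader might also infer that the trial is not analysed as randomised. The documents do not support that. Intention-to-treat is planned, and omitting a balanced factor with a continuous outcome causes neither bias nor excess false positives.

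The size is modest too. The top of the range assumes that past users differ by 16 points, as much as the whole treatment effect the trial is powered for, and no section gives evidence of any stratum difference. Finally, adjustment for baseline Skindex-29 does not follow from the label mismatch. It is a separate gain in precision made in the same sentence of the plan.

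**Conclusion.** The point holds as a free improvement, not as a fault in validity. The factor is labelled inconsistently, the t-test omits it, and no primary Skindex-29 analysis is named.

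Under 30–50% past users and an 8–16 point stratum difference, omission leaves the one-sided type I error at about 4.7% to 3.8% and forgoes about 0.7 to 3.3 points of power. With no prognostic effect the cost is nil. A broader steroid-history factor would recover part of the loss, so it cannot be called useless.

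A reader might set the adjusted power at the ends of this range (80.7% to 84.7%) against the 79.9% of Step 1 and read a gain of nearly 5 points. That is the wrong comparison: 79.9% ignores the blocking, and in the blocked trial the unadjusted test already gains something from the balance.

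All these sizes rest on the assumed f and d and on balance within strata. The gain from baseline adjustment is not quantified, because the documents give no correlation between baseline and follow-up scores.

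**What to change.** 1. In Section 12.0, name one primary Skindex-29 model: treatment, the randomisation stratum (past topical clobetasol, yes or no, as used at randomisation) and baseline Skindex-29.
2. Define the factor once and use the same label in Sections 3.0, 5.0 and 12.0, including the description of the randomisation list in Section 3.0.
3. Report the treatment-by-stratum interaction as secondary. If exposure to any steroid is of interest, define it separately and label it exploratory.

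The cost is wording. The Section 5.0 timeline already collects baseline Skindex-29. The stratum should exist in the randomisation records if the blocking was carried out as Section 5.0 describes, but the sponsor should confirm this because Section 3.0 does not mention it. No patients or visits are added, and the required sample size does not change.
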